1.4.2 Drug Information for Simvastatin

Simvastatin is an HMG-CoA reductase inhibitor (statin) indicated as an adjunctive therapy to diet to (per package insert):

- Reduce the risk of total mortality by reducing coronary heart disease (CHD) deaths and reduce the risk of non-fatal myocardial infarction, stroke, and the need for revascularization procedures in patients at high risk of coronary events.
- Reduce elevated total-C, LDL-C, Apo B, triglycerides (TG) and increase HDL-C in patients with primary hyperlipidemia (heterozygous familial and nonfamilial) and mixed dyslipidemia.

- Reduce elevated triglycerides (TG) in patients with hypertriglyceridemia and reduce TG and VLDL-C in patients with primary dysbetalipoproteinemia.
- Reduce total-C and LDL-C in adult patients with homozygous familial hypercholesterolemia.
- Reduce elevated total-C, LDL-C, and Apo B in boys and postmenarchal girls, 10 to 17 years of age with heterozygous familial hypercholesterolemia after failing an adequate trial of diet therapy.

We will monitor patient lipids to ensure adequate levels of HDL.

Limitations of Use – Simvastatin has not been studied in Fredrickson Types I and V dyslipidemias.

The use of simvastatin is contraindicated with the administration of strong CYP3A4 inhibitors and gemfibrozil, cyclosporine, or danazol. It is also not to be used in patients with hypersensitivity to any component of this medication, active liver disease, and with elevations in hepatic transaminase levels. It is also recommended that the dose of simvastatin not exceed 10 mg daily if patients are taking verapamil, diltiazem, and dronedarone. Simvastatin should not exceed 20 mg daily if patients are taking amiodarone, amlodipine, and ranolazine. Women who are pregnant or may become pregnant or are nursing mothers should not take simvastatin. All patients should avoid grapefruit juice.

Most common adverse reactions (incidence $\geq 5.0\%$) are: upper respiratory infection, headache, abdominal pain, constipation, and nausea.

Patients should be advised of the increased risk of myopathy: rhabdomyolysis has been seen in patients taking the 80 mg dose.

Simvastatin dosing ranges from 5 mg to 40 mg once daily. The typical starting dose is 10 mg or 20 mg once a day in the evening. The recommended starting dose for patients at high risk of CHD is 40 mg/day.

2. Objectives and Specific Aims

2.1 Objectives

The hypothesis to be tested is whether simvastatin can be safely added to the treatment of LAM-S or LAM-TS patients who have been on a stable (for at least three months) dose of mTOR inhibitors either sirolimus or everolimus. Specific objectives are:

Primary:

- Safety of simvastatin in the treatment of LAM-S and LAM-TS patients on a stable (for at least 3 months) dose of sirolimus or everolimus

Secondary:

- To assess the effect of simvastatin on forced expiratory volume in 1 second (FEV₁).
- To assess the effect of simvastatin on forced vital capacity (FVC).
- To assess the effect of simvastatin on diffusing lung capacity (DLCO).
- To assess the effect of simvastatin on VEGF-D serum levels.
- To assess the effect of simvastatin with questionnaire-based assessments of dyspnea, fatigue, and quality of life (QOL)) using the **St. George's Respiratory Questionnaire (SGRQ) and the Functional Performance Inventory (FPI)**.
- To preliminarily assess effectiveness and clinical benefit in this patient population.

2.2 Specific Outcomes

2.2.1 Primary Outcome

The primary outcome will be to determine if simvastatin can be used safely in the treatment of LAM-S or LAM-TS patients on sirolimus or everolimus.

2.2.2 Secondary Outcome

Secondary outcome measures will include effect of simvastatin addition to mTOR inhibitor therapy, either sirolimus or everolimus, on forced expiratory volume in one second (FEV₁), forced vital capacity (FVC), diffusing lung capacity (DLCO), serum VEGF-D levels, questionnaire based assessments of dyspnea, fatigue, and quality of life (QOL), and clinical benefit. The final analysis will occur after the last actively enrolled patient has completed the four month study visit.

3. Study design

This is an open label, non-randomized, dose-escalation study conducted as a pilot safety study. Patients will continue on their existing background therapy of either sirolimus or everolimus for treatment of their LAM or LAM-TS disease. Each patient is anticipated to participate in the study for approximately 5.5 months (approximately 164 days).

3.1 Identification and screening

Patients will be identified by the medical staff that care for patients with LAM-S and LAM-TS at the LAM clinic at the University of Pennsylvania Health System. Study staff expect to screen up to 10 patients over 3-6 months. Potentially eligible patients will be approached by their physician, and then by study staff. Potential patients will be informed about the study, and following completion of the informed consent process, a

screening evaluation will be performed. The patient will provide informed consent *before* any study procedures are performed.

3.2 Patient selection criteria

3.2.1 Inclusion criteria

- Female, age 18 and older with clinically definitive diagnosis (biopsy proven or compatible chest CT/MRI scan) of sporadic LAM (LAM-S) or LAM associated with TS (LAM-TS). Treated with a stable (at least 3 months) dose of sirolimus or everolimus
- Treated with a stable (at least 3 months) dose of sirolimus or everolimus
- Negative pregnancy test (women of child bearing potential) at screening.
- Women of childbearing potential must be using barrier, medically acceptable contraceptive precautions.
- Signed and dated informed consent.

3.2.2 Exclusion criteria

- Age < 18 years
- Known allergy to simvastatin or currently taking simvastatin, or therapy with a medication in the same class as simvastatin within the past 30 days.
- Allergy to sirolimus or everolimus.
- Current use of other than sirolimus or everolimus investigational drug for TSC or LAM within the past 30 days.
- Use of estrogen containing medications, including birth control pills, within the 30 days prior to enrollment.
- Treatment within 30 days of screening with drugs having known metabolic interactions with statin drugs, including:
 - strong CYP3A4 [cytochrome P450 3A4 metabolism] inhibitors (such as itraconazole, ketoconazole, posaconazole, voriconazole, fluconazole, azithromycin, erythromycin, clarithromycin, etc), gemfibrozil, cyclosporine, danazol, verapamil, diltiazem, dronedarone, amiodarone, amlodipine, ranolazine, lomitapide, and other lipid lowering medications (such as niacin [nicotinic acid], digoxin, warfarin, sildenafil, etc)
- Participation in another clinical study(ies) of an investigational treatment or drug within 30 days prior to the screening visit.
- Significant dysfunction of liver (ALT > 2X ULN), kidney (serum creatinine > 1.5X ULN), or blood (leucopenia (ANC<2000), anemia, Hgb < 11 gm/dl).
- History of inflammatory muscle disease or myopathy.
- Bleeding diathesis or anticoagulant therapy.

- Uncontrolled hyperlipidemia or diabetes.
- Pregnant, breast feeding, or plan to become pregnant within the next 6 months
- Inadequate contraception (must agree to barrier method)
- History of organ transplant.
- Active on transplant list.
- Severe or uncontrolled medical conditions which would cause an unacceptable safety risk or compromise compliance with the protocol.
- Unstable seizures (recent changes in pattern or anti-epileptics).
- Mental illness or cognitive deficit precluding informed consent.
- Inability to attend scheduled clinic visits or comply with study procedures.

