OBJECTIVES:	
The primary objective of this study is to determine the safety of simvastatin in the treatment of LAM-S or LAM-TS in patients on a stable (for at least 3 months) dose of sirolimus or everolimus.
 
Secondary objectives include:
 
• To assess the effect of simvastatin on forced expiratory volume in 1 second (FEV₁).• To assess the effect of simvastatin on forced vital capacity (FVC).• To assess the effect of simvastatin on diffusing lung capacity (DLCO).• To assess the effect of simvastatin on VEGF-D serum levels.• To assess the effect of simvastatin with questionnaire- based assessments of dyspnea, fatigue, and quality of life (QOL) using the St. George's Respiratory Questionnaire (SGRQ) and the Functional Performance Inventory (FPI).

[figure not shown]
- Preliminarily assess effectiveness and clinical benefit in this patient population.

TREATMENT:

Agent:	Simvastatin
Dosage, schedule, route of administration:	Dose escalation from 20 mg once-daily (QD) for the first two months to 40 mg QD for months 3 and 4. The study drug will be given orally.
Safety Issues:	Simvastatin, a cholesterol lowering agent, is effective in preventing cardiovascular diseases. Concomitant administration of strong CYP3A4 inhibitors, gemfibrozil, cyclosporine, or danazol is contraindicated. Simvastatin is not to be used in patients with myopathy, hypersensitivity to any component of the medication, active liver disease, pregnant women, or nursing mothers. The most commonly experienced adverse events with simvastatin are: rhabdomyolysis, upper respiratory infection, headache, abdominal pain, constipation, and nausea.
Primary Outcome Measures:	Safety of simvastatin in the treatment of LAM-S and LAM-TS patients on a stable (for at least 3 months) dose of sirolimus or everolimus.
Secondary Outcome Measures:	FEV1, FVC, DLCO, VEGF-D, and QOL; signs of clinical benefit.
Statistical Considerations (sample size and analysis plan):	Up to 10 evaluable patients will be enrolled and treated with increasing doses of simvastatin for 120 days. We anticipate a 10% attrition rate. The analysis will be based on an intention to treat design. The final analysis will occur after the last enrolled patient has completed the 120 day visit.
Sponsors (federal, state, foundation and industry support):	LAM Foundation

STUDY DESIGN:

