Simvastatin has been evaluated for adverse reactions in over 21,000 patients; only 1.4% discontinued therapy due to adverse experience. Rhabdomyolysis and elevations in serum transaminases are the two main side effects of simvastatin. Large clinical trials have shown no significant differences in the incidence of elevated creatine phosphokinase (CPK) 4-10X the upper limit of normal (ULN) between simvastatin (0.19%) and placebo (0.13%) or myopathy (CPK > 10X ULN) (5). The number of subjects with elevated transaminases (2-4X ULN) was also small and no different than placebo (1.35% for simvastatin, 1.28% for placebo, p=NS) (5). Treatment cessation due to this complication was comparable between the groups (0.5% for simvastatin, 0.3% for placebo).

Patients who are eligible will receive instructions for simvastatin and the initial one month supply. Patients will be instructed to take simvastatin in the evening and advised to avoid grapefruit juice due to the potential for an interaction. Patients will be reminded about the side effects of simvastatin, and will be given a drug information sheet, including all adverse drug interactions.

Patients will be carefully monitored at visits 3, 4, 5 and 6 for signs and symptoms of simvastatin side effects including upper respiratory infection, headache, abdominal pain, constipation, and nausea.

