3.5.1 Treatment Regimen

We have chosen an intra-patient dose escalation strategy because there is no previous data from human studies to demonstrate the safety of simvastatin in combination with sirolimus or everolimus, in patients with LAM-S and LAM-TS. Dose escalation strategy will be performed only for patients who tolerate 20 mg daily simvastatin. If patients do not tolerate the 20 mg simvastatin dose, the dose will be down-titrated to 10 mg daily. If 20 mg daily is well tolerated, at visit 4 the dose will be increased to 40 mg daily for months 3 and 4. If 40 mg daily is not well tolerated, the dose will be reduced back to 20 mg daily.

Intermediate dose reductions to 15 or 30 mg/day may be undertaken if the side effect(s) is reasonably mild and tolerable.

[figure not shown]
Patients will remain on their current dose of sirolimus or everolimus without interruption, as clinically indicated.

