4.2 Study schedule of procedures

The table below summarizes the study procedures.

Table 1: Study Procedures

Event	Screen	Day 0	Day 30	Day 60	Day 90	Day 120
Visit number	1	2	3	4	5	6
Informed consent	X		-	-	-	-
History and physical	X		X	X	X	X
Chest X-ray	X					X
Blood levels of sirolimus (target range 3-20 ng/ml) or everolimus (target range of 3-20 ng/ml)	X		X	X	X	X
CBC, CPK, CMP *	X		X	X	X	X
Lipid profile**	X		X	X	X	X
VEGF-D		X	X	X	X	X
Saved serum and plasma		X	X	X	X	X
Urine pregnancy test	X	X	X	X	X	X
Spirometry (FEV1, FVC DLCO)		X		X		X

Review concomitant medications	X	X	X	X	X	X
Review adverse events			X	X	X	X
Study drug (simvastatin) management		X	X	X	X	X
SGRQ and FPI		X	X	X	X	X

*CMP to include BUN, creatinine, ALT, AST, Alk Phos, total bilirubin

**Lipid Panel to include total cholesterol, LDL, HDL and triglycerides.

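### The liver exclusion limits ALT only and omits active liver disease, although the protocol's own safety text bars simvastatin in active liver disease or with raised transaminases

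*Combined protocol and SAP*

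**What the plan says.** Section 3.2.2 and the matching list in the Protocol Summary give the same organ-function exclusion: "Significant dysfunction of liver (ALT > 2X ULN), kidney (serum creatinine > 1.5X ULN", followed by blood-count limits. ALT is the only liver test with a limit. Active liver disease does not appear in either list. The nearest other item is a general one: "Severe or uncontrolled medical conditions which would cause an unacceptable safety risk or compromise compliance with the protocol".

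The drug-safety text is broader. The Safety Issues entry of the Protocol Summary says simvastatin is "not to be used in patients with myopathy, hypersensitivity to any component of the medication, active liver disease, pregnant women, or nursing mothers". Section 1.4.2 adds raised transaminases; its list of patients who should not receive the drug includes those with "active liver disease, and with elevations in hepatic transaminase levels". It gives no multiple of ULN.

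The screening panel goes beyond ALT. The footnote to Table 1 in Section 4.2 reads "CMP to include BUN, creatinine, ALT, AST, Alk Phos, total bilirubin".

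**The concern.** An entry rule should be at least as strict as the contraindications that the same protocol states for its study drug. Here it is looser. Taken literally, the exclusion list admits patients whom the safety text says must not receive simvastatin.

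The liver matters for this drug. Section 1.4.1 names transaminase elevation as one of its two main side effects, and Section 5.2.3 names it among the main laboratory abnormalities to expect. Section 1.4.1 also says that simvastatin and the mTOR inhibitors share a hepatic CYP3A4 route. Section 3.5.1 gives the reason for caution: for LAM patients, "there is no previous data from human studies to demonstrate the safety of simvastatin in combination with sirolimus or everolimus". Safety is the primary outcome. A patient who enters with a raised AST is exposed to avoidable risk, and any later liver signal in her would be harder to attribute to simvastatin.

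**Working it through.** The check is mainly a comparison of texts. Arithmetic is needed only for the cost of the fix.

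**1. Are the stated contraindications carried into the exclusion list?** The Safety Issues entry names five conditions.

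| Condition barred in Safety Issues | Named in Section 3.2.2? |
|---|---|
| Myopathy | Yes |
| Hypersensitivity | Yes, as known allergy to simvastatin |
| Active liver disease | No; only the ALT limit |
| Pregnancy | Yes |
| Nursing | Yes |

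Four of the five are carried over by name. The contraindicated drugs (strong CYP3A4 inhibitors, gemfibrozil, cyclosporine, danazol) are carried over too. Active liver disease is the one left out, and the protocol gives no reason.

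**2. Which screening liver tests have an entry limit?** ALT has one (2X ULN). AST, alkaline phosphatase and total bilirubin have none. Of the two transaminases, 1 of 2 is limited.

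**3. Who passes the list but falls under the prohibition?**
- ALT at or below 2X ULN with AST raised to any level: passes the liver item; barred by Section 1.4.2.
- Active liver disease, not severe or uncontrolled, with ALT at or below 2X ULN: passes; barred by Safety Issues and by Section 1.4.2.
- ALT between 1X and 2X ULN: passes; barred only if any value above ULN counts as an elevation. Section 1.4.2 does not say so, and Section 1.4.1 reports elevations from 2X upward ("The number of subjects with elevated transaminases (2-4X ULN) was also small"). The 2X limit is therefore not challenged here.

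**4. What controls the first dose?** Section 4.3.2 (Day 0) requires a review of screening tests and confirmation of eligibility, then dispensing of 20 mg. It has no separate contraindication check. The 40 mg step at Visit 4 (Section 4.3.4) does carry such a caveat.

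**5. What follows the first dose?** Table 1 next schedules chemistry at Day 30. Section 5.2.3 then sets specific follow-up and stopping rules for CPK but none for transaminases, which leaves the general hold for related events of Grade 3 or higher.

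**6. What could the fix cost in information?** Section 3.1 says "Study staff expect to screen up to 10 patients over 3-6 months", and the enrolment ceiling is also 10. Take the worst case: one extra screen failure, not replaced, with everyone else eligible and the 10% attrition of Section 11.1.
- Evaluable now: 10 × 0.9 = 9.
- Evaluable with one fewer enrolled: 9 × 0.9 = 8.1, about 8.
- Probability of seeing no DLT at true rate p among n patients: (1 − p)^n.

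| True DLT rate | n = 9 | n = 8 |
|---|---|---|
| 11% | 0.89^9 = 35.0% | 0.89^8 = 39.4% |
| 22% | 0.78^9 = 10.7% | 0.78^8 = 13.7% |
| 33% | 0.67^9 = 2.7% | 0.67^8 = 4.1% |

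The n = 9 column reproduces the last row of Table 5 for these rates.

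**The case against.** The best reply is that the protocol already protects these patients. The Safety Issues entry sits in the treatment block of the Protocol Summary and is directive, so a patient with active liver disease may not be given the drug whatever the checklist says. Clinicians must review the screening tests before Day 0 dispensing and will see the AST. The general medical-conditions exclusion gives them a ground to refuse. The contraindication caveat at Visit 4 may be there simply because eligibility is not formally rechecked at that visit. Listing active liver disease still leaves a clinical judgment. No AST threshold appears anywhere in the documents, so 2X ULN for AST is a choice. Section 1.4.1 also reports transaminase elevations at nearly the same rate on simvastatin and placebo (1.35% and 1.28%).

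Much of this stands, and it limits the size of the gap. It does not close it. Reviewing a result is not the same as having a limit to apply to it, and the general exclusion need not catch an isolated AST rise or mild active disease. The AST threshold is a choice, but it extends to the second transaminase the limit already accepted for the first. The placebo comparison is not presented as evidence on the combination with an mTOR inhibitor. None of these points supplies an AST limit or explains why one of five stated contraindications is missing from the list that staff must confirm.

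**Conclusion.** The concern holds. The entry rule as written is looser than the protocol's own contraindications, in two respects: AST has no limit, and active liver disease is not listed. Neither point depends on how an elevation is defined between 1X and 2X ULN; the AST point assumes only that a marked rise in AST counts as a transaminase elevation under Section 1.4.2.

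This is a small patient-safety gap at entry. The documents give no frequency for raised AST, or for active liver disease, with ALT at or below 2X ULN in LAM, so the number affected cannot be estimated and may be zero among up to 10 patients. The DLT definition, the planned sample size and Table 5 do not change. The correction is recommended because it costs almost nothing and aligns the protocol with its own safety text.

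**What to change.** In Section 3.2.2 and in the exclusion list of the Protocol Summary, change the liver limit to *ALT or AST > 2X ULN* and add *active liver disease* as an exclusion. Keep the 2X multiple. The AST limit is an objective check on a result already in hand. Active liver disease remains a clinical judgment, made at the screening history and physical examination (Section 4.3.1), but listing it makes that judgment part of the eligibility review before the first dose.

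The cost is wording in two places and no new test. The possible downside is an extra screen failure, with the worst case calculated above (at an 11% true rate, 39.4% instead of 35.0% chance of seeing no DLT). That is avoidable: the 10 in Section 3.1 is an expected number to screen, not a stated cap, so one more patient can be screened.

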3.3 Recruitment

After IRB approval has been obtained, the LAM community will be notified about the existence of the study by postings in public places and on the internet,. Patients will also be referred by physicians and LAM support groups such as the LAM Foundation, and the Tuberous Sclerosis Alliance. The study will be posted on clinicaltrials.gov.

3.4 Enrollment

Potential study patients will be contacted by the study staff to determine interest in study participation. Contact may be made by postal mail, electronic mail or in person. Interested individuals will receive study information, including a cover letter and a consent form. Patients may be consented and preliminarily assessed prior to the actual screening visit.

All patients enrolled will be female. Up to ten evaluable patients will be enrolled. As in prior studies, an attrition rate of 10% is expected; appropriate adjustments will be made in the number of enrolled patients.

3.5 Study drug treatment

Patients who meet eligibility criteria, provide informed consent and are enrolled in the study will receive instructions regarding simvastatin dosage, route and administration. A one month supply of simvastatin 20 mg will be provided at visit 2.. Patients will be reminded about the side effects of simvastatin, and will be given a drug information sheet. Patients will be instructed to take the study medication in the evening every day. Patients will be carefully monitored monthly at visits 3, 4, 5 and 6 for signs and symptoms of simvastatin side effects including: upper respiratory infection, headache, abdominal pain, constipation, myalgias, arthralgias and nausea. Patients will be instructed to contact the study staff should they experience any of these side effects. Simvastatin doses may be held or reduced in the event of unacceptable side effects.

3.5.1 Treatment Regimen

We have chosen an intra-patient dose escalation strategy because there is no previous data from human studies to demonstrate the safety of simvastatin in combination with sirolimus or everolimus, in patients with LAM-S and LAM-TS. Dose escalation strategy will be performed only for patients who tolerate 20 mg daily simvastatin. If patients do not tolerate the 20 mg simvastatin dose, the dose will be down-titrated to 10 mg daily. If 20 mg daily is well tolerated, at visit 4 the dose will be increased to 40 mg daily for months 3 and 4. If 40 mg daily is not well tolerated, the dose will be reduced back to 20 mg daily.

Intermediate dose reductions to 15 or 30 mg/day may be undertaken if the side effect(s) is reasonably mild and tolerable.

[figure not shown]
Patients will remain on their current dose of sirolimus or everolimus without interruption, as clinically indicated.

